5.3 Dose Expansion Cohort

Once the RP2D is reached, an additional 15 patients will be treated at this dose to further explore pharmacodynamic endpoints and obtain additional pharmacokinetic data. For the expansion cohort, patients will continue to be monitored for occurrence of toxicities that meet the definition DLT after cycle 1. Once pharmacodynamic data are available, additional expansion cohorts may be considered to explore pharmacodynamic endpoints at lower dose levels (a protocol amendment will be submitted for these changes to the trial design).

5.4 General Concomitant Medication and Supportive Care Guidelines

All patients will be provided with the best available supportive care. All concurrent medications should be documented prior to initiation of treatment and periodically reviewed with the patient.

It is not known which CYP enzymes are involved in the metabolism of CB-5339, and CB-5339 appears to be a potential inhibitor of **CYP2C19** and 2C9 in vitro. Therefore, for patients enrolled in the dose-escalation phase, avoid concomitant use of drugs that are strong inhibitors of CYP enzymes during the dose escalation phase, and substrates of CYP2C19 and 2C9 with narrow therapeutic indices, as this may affect the determination of the recommended phase 2 dose.

During the expansion phase, any concomitant use of CB-5339 and drugs that are strong inhibitors of CYP enzymes or substrates with narrow therapeutic indices for CYP2C19 (e.g., diazepam) or CYP2C9 (e.g., warfarin, phenytoin, many sulfonylureas (tolbutamide, glyburide, glibenclamide, glipizide, glimepiride) will be monitored closely. Consult <http://medicine.iupui.edu/flockhart/> for frequently updated information on drug interactions with cytochrome P450 isoenzymes.

Patients on study may be eligible for palliative radiotherapy to non-targeted lesions after completing 2 cycles of therapy at the Principal Investigator's discretion.

- 5.4.1 Nausea/Vomiting: Anti-emetics will not be administered routinely prior to CB-5339. However, if a patient develops nausea/vomiting, anti-emetics such as but not limited to prochlorperazine, metoclopramide, 5-HT3 antagonists, or aprepitant may be given. In addition, if a patient develops nausea and/or vomiting that is Grade 2 or greater, anti-emetics may be instituted prophylactically at the discretion of the investigator. Nausea and vomiting will be considered refractory if it does not resolve to grade 2 or less with a combination of at least 2 anti-emetics within 24 hours.
- 5.4.2 Diarrhea: Subjects will not be given anti-diarrhea medication prophylactically. If diarrhea develops and does not have an identifiable cause other than study drug administration, addition of anti-motility agents such as tincture of opium (deodorized 10%), Lomotil (diphenoxylate HCl 2.5 mg + atropine sulfate 0.025 mg/tablet) dosed according to the package insert, or loperamide 4 mg po after the first unformed stool with 2 mg po with every 2 hours as long as unformed stools continue (4 mg every 4 hours while asleep) may be used. No more than 16 mg of loperamide should be taken during a 24-hour period). This regimen can be repeated for each diarrheal episode and will continue for 12 hours after the first formed stool. Diarrhea will be considered refractory if it does not resolve within 24 hours \leq to Grade 2 with the above measures. If the patient develops blood or mucus in the stool, dehydration, or hemodynamic instability, or fever along with the diarrhea, anti-diarrheals will be discontinued and the patient will be treated with IV fluids and antibiotics as medically indicated. Other potentially helpful treatments may also be administered, such as somatostatin analogues, propantheline bromide, etc.
- 5.4.3 Electrolyte Abnormalities: If hypokalemia, hypophosphatemia, or

hypomagnesemia occur, the patient may receive oral or IV supplementation to correct the abnormality. If hyponatremia occurs, the patient may receive 0.9% sodium chloride intravenously to correct the abnormality.

- 5.4.4 Neutropenia: Febrile neutropenia is a life-threatening complication requiring hospitalization and urgent broad-spectrum antibiotics, as well as an aggressive search for the source and microbial cause of the episode. If clinically indicated, filgastrim will be administered according to accepted guidelines (ASCO or Clinical Center). Study medication will not be reinitiated until at least 24 hours after filgrastim administration.
- 5.4.5 Anemia: Symptomatic anemia should be treated with red blood cell transfusion and is recommended if the hemoglobin falls below 8 g/dL. The initiation of erythropoietic therapy for the management of chemotherapy-induced anemia follows the American Society of Hematology/ASCO clinical practice guidelines (<http://www.asco.org>).
- 5.4.6 Thrombocytopenia: Thrombocytopenia will be treated conservatively. In the absence of bleeding, or a necessary invasive procedure, platelet transfusions should be given for a platelet count $\leq 10,000/\text{mm}^3$. If invasive procedure(s) is (are) planned, or the patient develops bleeding, platelet transfusions should be administered in accordance with the standard of practice, usually maintaining a platelet count above $50,000/\text{mm}^3$.

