3.2 Exclusion Criteria

- 3.2.1 Patients who have had chemotherapy or radiotherapy within 4 weeks (6 weeks for nitrosoureas or mitomycin C) prior to entering the study.
- 3.2.2 Patients who have not recovered from adverse events due to prior anti-cancer therapy (i.e., have residual toxicities $>$ Grade 1) with the exception of alopecia.
- 3.2.3 Patients who are receiving any other investigational agents.
- 3.2.4 Patients with clinically significant illnesses which would compromise participation in the study, including but not limited to active or uncontrolled infection, immune deficiencies, Hepatitis B, Hepatitis C, active tuberculosis, uncontrolled asthma, symptomatic congestive heart failure, unstable angina pectoris, uncontrolled cardiac arrhythmia, myocardial infarction within the past 6 months, cerebral vascular accident/stroke within the past 6 months, or psychiatric illness/social situations that would limit compliance with study requirements.
 - Human immunodeficiency virus (HIV)-infected patients on effective anti-retroviral therapy with undetectable viral load within 6 months are eligible for this trial.
 - For patients with evidence of chronic hepatitis B virus (HBV) infection, the HBV viral load must be undetectable on suppressive therapy, if indicated.
- 3.2.5 Patients with known brain metastases or carcinomatous meningitis are excluded from this clinical trial, with the exception of patients whose brain metastatic disease status has remained stable for \geq 4 weeks after treatment of the brain metastases. Patients on anti-seizure medications may be enrolled at the discretion of the Principal Investigator providing that these patients are taking non-enzyme- inducing anti-seizure medications or can be converted to these.
- 3.2.6 Pregnant women are excluded from this study because CB-5339 may have the potential for teratogenic or abortifacient effects. Because there is an unknown but potential risk for adverse events in nursing infants secondary to treatment of the mother with this agent, breastfeeding should be discontinued if the mother is treated with CB-5339.

- 3.2.7 Current or previous history of sight-threatening retinal disease, including (but not limited to) proliferative diabetic retinopathy, severe retinal vascular disease, and advanced age-related macular degeneration.
- 3.2.8 Patients with a history of QT-prolongation or of Torsades de pointes (TdP), or of taking QT-prolonging drugs, are not eligible.

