5.2 Definition of Dose-Limiting Toxicity

Determination of dose-limiting toxicity (DLT) will be based on toxicities observed in the first cycle of therapy and felt to be at least possibly related to study drug. A greater than 2-week delay for AEs before cycle 2 would be considered a DLT.

This study will follow design 3 of the Simon accelerated titration designs (Simon et al., 1997). We will accrue to the next dose level only after we have established safety at lower dose levels.

During this accelerated phase, there will be one patient per dose level. After the first instance of a drug-related Grade 2 toxicity (during the first cycle) at any dose level, the accelerated phase will end, and dose escalation will be changed to a 3 + 3 design. All decisions on dose expansion and DLT will be made on the first cycle of treatment.

When the accelerated phase ends, the trial will go back to a traditional 3+3 design. That is, additional patients will be placed on the dose level at which the last new patient was treated; 3 patients will be treated initially at each new dose level.

Number of Patients with DLT at a Given Dose Level	3+3 Escalation Decision Rule
0 out of 3	Enter 3 patients at the next dose level.
≥ 2	Dose escalation will be stopped. This dose level will be declared the maximally administered dose (highest dose administered). Three (3) additional patients will be entered at the next lowest dose level if only 3 patients were treated previously at that dose.
1 out of 3	Enter at least 3 more patients at this dose level. 
• If 0 of these 3 patients experience DLT, proceed to the next dose level.• If 1 or more of this group suffer DLT, then dose escalation is stopped, and this dose is declared the maximally administered dose. Three (3) additional patients will be entered at the next lowest dose level if only 3 patients were treated previously at that dose.
≤ 1 out of 6 at highest dose level below the maximally administered dose	This is generally the recommended phase 2 dose. At least 6 patients must be entered at the recommended phase 2 dose.

If ≥ 2 patients experience DLT on dose level -1, the study will be placed on hold and all data reviewed to make a decision about further evaluation of the study drug.

DLT is defined as an adverse event that is related (possibly, probably, or definitely) to

administration of study drug and fulfills one of the following criteria:

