Route of administration: oral; capsules should be taken on an empty stomach (i.e., either 1 hour before or 2 hours after meals) with water.

Potential Drug Interactions: *In vitro* studies suggest CB-5339 tosylate is hepatically metabolized, with metabolic pathways not fully defined.

In vitro, CB-5339 tosylate showed moderate inhibition of CYP2C9 and CYP2C19, and weak inhibition of CYP1A2 and CYP2D6. CB-5339 tosylate did not inhibit CYP3A4. Use caution when co-administered with CYP2C9 and CYP2C19 substrates.

In vitro, CB-5339 tosylate is > 98% protein-bound in human plasma. Use caution when co-administered with other medications that are highly protein-bound.

Patient Care Implications: CB-5339 tosylate must not be administered to pregnant or nursing females. Women study participants of reproductive potential and fertile men study participants and their partners must abstain or use effective contraception while receiving study treatment and for at least 4 months after the last dose.

Availability: CB-5339 is an investigational agent supplied to investigators by the Division of Cancer Treatment and Diagnosis (DCTD), NCI. CB-5339 is provided to the NCI under a Collaborative Agreement between the Pharmaceutical Collaborator and the DCTD, NCI (see Section 12.3).

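### Section 5.4 bars strong CYP inhibitors during dose escalation to protect the RP2D but says nothing about strong CYP inducers, which could lower exposure and hide toxicity

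*Combined protocol and SAP*

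**What the plan says.** Section 5.4 says it is unknown which CYP enzymes metabolize CB-5339. Section 6.1 adds that in vitro work suggests "CB-5339 tosylate is hepatically metabolized, with metabolic pathways not fully defined". From that premise 5.4 tells investigators, for patients in escalation, to "avoid concomitant use of drugs that are strong inhibitors of CYP enzymes during the dose escalation phase", along with narrow-index substrates of CYP2C19 and CYP2C9, "as this may affect the determination of the recommended phase 2 dose". In expansion the same classes are allowed but watched closely. Neither paragraph of 5.4 mentions inducers, and neither does the interaction text in 6.1.

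Two other provisions bear on the point:

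- Exclusion 3.2.5, within the brain-metastasis criterion, lets patients on anti-seizure drugs enroll if they are "taking non-enzyme- inducing anti-seizure medications or can be converted to these".
- Section 5.4 also requires that "All concurrent medications should be documented prior to initiation of treatment and periodically reviewed with the patient".

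On the design, Section 5.2 states: "During this accelerated phase, there will be one patient per dose level". The accelerated phase ends "After the first instance of a drug-related Grade 2 toxicity (during the first cycle) at any dose level". Section 7.1 sends samples from the first three patients for real-time PK, but also says PK will not determine escalation or expansion doses.

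**The concern.** The sponsor's argument is that if the clearing enzymes are unknown, a co-medication that changes CYP activity could shift exposure and mislead the choice of RP2D. That argument has no preferred direction. An inhibitor could raise exposure and make a dose look too toxic; an inducer could lower exposure and make it look safer than it is. The rule guards against the first error and leaves the second open.

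The open one is the error that matters most for escalation. At an accelerated level one patient decides, so if that patient is induced, the Grade 2 event that should switch the trial to 3+3 may not appear. In the 3+3 phase, an induced patient makes it more likely that a level above the true MTD clears. Intra-patient escalation (Section 5.2) is allowed up to the last evaluated level without DLT, so a level cleared this way also opens that dose to patients already on study. Because 7.1 keeps PK out of dose decisions, a low measured exposure has no stated role in holding back the next level.

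**Working it through.** **Text check.** The plan's provisions against the gap:

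| Provision | What it does about strong inducers |
|---|---|
| 5.4, escalation | Bars strong inhibitors and narrow-index CYP2C19/2C9 substrates; inducers not named |
| 5.4, expansion | Monitors the same classes; inducers not named |
| 5.4, phenytoin | Listed as a CYP2C9 substrate, so caught in escalation on that ground; other inducers are not |
| 6.1 | Caution for CYP2C9/2C19 substrates and highly protein-bound drugs; inducers not named |
| 3.2.5 | Anti-seizure drugs only, as an enrollment criterion |
| 5.4, medication review | Would record an inducer; does not bar it |

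The plan gives no figure to reproduce.

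**Illustration.** The documents give neither the effect of induction on CB-5339 nor the frequency of inducer use. Every rate below is an assumption; only the decision rule and patient numbers come from the protocol.

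*3+3 level (rule from 5.2: escalate on 0 of 3, or on 1 of 3 followed by 0 of 3).*

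P(clear) = (1−p)³ + 3p(1−p)² × (1−p)³

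With an assumed true DLT rate p = 0.33: 0.3008 + 0.4444 × 0.3008 = 0.434.

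Let each patient be on a strong inducer with probability q, with DLT risk 0.10 if induced, so p_eff = 0.33(1−q) + 0.10q:

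| q | p_eff | P(clear) | Rise (points) |
|---|---|---|---|
| 0.02 | 0.3254 | 0.443 | 0.9 |
| 0.05 | 0.3185 | 0.457 | 2.3 |
| 0.10 | 0.3070 | 0.480 | 4.6 |

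Varying the induced risk from 0.05 to 0.15 widens the rise to 0.7 (risk 0.15, q = 0.02) through 5.6 points (risk 0.05, q = 0.10).

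*Given that exactly one of the first three patients is induced (risk 0.10):*

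- P(0 DLT) = 0.67² × 0.90 = 0.4040
- P(1 DLT) = 0.10 × 0.67² + 0.90 × 2 × 0.33 × 0.67 = 0.4429
- P(clear) = 0.4040 + 0.4429 × 0.3008 = 0.537

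This is 0.560 at induced risk 0.05 and 0.515 at 0.15.

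*Accelerated level (one patient; assumed rate of Grade 2 or worse 0.50, or 0.20 if induced).*

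P(no trigger) = 1 − [0.50(1−q) + 0.20q] = 0.506, 0.515 and 0.530 for q = 0.02, 0.05 and 0.10, against 0.50 with no inducer use. If that one patient is induced, it is 0.80.

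*Chance that at least one escalation patient is induced,* 1 − (1−q)ⁿ, with n = 6 to 18 from Section 8.2:

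| q | n = 6 | n = 18 |
|---|---|---|
| 0.02 | 0.114 | 0.305 |
| 0.05 | 0.265 | 0.603 |
| 0.10 | 0.469 | 0.850 |

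The average effect is small because inducer use is assumed uncommon. The effect at a level where an induced patient is actually treated is not small.

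**The case against.** The case against has several sound parts.

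- **Existing cover.** 3.2.5 handles enzyme-inducing anti-seizure drugs, and its conversion clause suggests patients would stay on the non-inducing drug. Phenytoin is avoided in escalation as a narrow-index CYP2C9 substrate. Exclusion 3.2.4 removes active tuberculosis and uncontrolled infection, which makes anti-infective inducers less likely. Use at 10% may therefore be a high assumption.
- **Later checks.** Section 2.3 makes attained exposure one of three RP2D determinants. Day 1 PK is collected from every patient. Section 5.3 adds 15 patients at the RP2D with continued monitoring for DLT-type toxicity. The Grade 2 trigger works at every level, so one missed at a given level may fire at the next, and no step more than doubles the dose. Section 12.1 requires investigator sign-off and at least monthly calls with the CTEP medical officers.
- **Unproven harm.** With the pathway unknown, no induction effect on CB-5339 is established. Putting inhibitors first in a first-in-human trial is reasonable, because they endanger the patient directly.
- **Appendix F.** The drug-interaction handout is in the contents list but was not available to this review, and it may mention inducers.

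These points limit the likely damage. They do not close the gap: none bars a strong inducer other than an anti-seizure drug during escalation, and the exposure and expansion checks act after levels have been cleared. The unknown pathway is also the sponsor's own reason for barring inhibitors. Appendix F is a patient handout; even if it covers inducers, the investigator rule in 5.4 would still need to match it.

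**Conclusion.** The concern holds. Section 5.4 applies its own rationale in one direction only, and the escalation rule as written admits a class of drugs that could mask the Grade 2 or DLT signal. On the assumed rates the average distortion is modest: 0.7 to 5.6 points on a 43.4% chance of clearing a 3+3 level, and 0.6 to 3.0 points on a 50% chance of no trigger at an accelerated level. At a level where an induced patient is treated it is material: 51–56% (induced patient among the first three) and 80% respectively. These figures depend wholly on assumed DLT, Grade 2 and inducer-use rates, and on induction lowering CB-5339 exposure, which is plausible but not shown.

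The consequence for the final dose is bounded by the rule that "At least 6 patients must be entered at the recommended phase 2 dose". Sample size, alpha and power are unaffected. The change should be made, with medium confidence in its practical importance.

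**What to change.** In Section 5.4, add strong CYP inducers to the drugs to avoid during dose escalation, and to the drugs monitored closely during expansion. The clinical team should decide which drugs count as strong inducers. Confirm that Appendix F says the same.

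The cost is one phrase in each of two sentences and a check of the handout. The downside is slightly tighter co-medication limits for escalation patients.
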